## 6.6.2.2. Continuous Secondary Endpoints with MMRM Model

### 6.6.2.2.1.1. Estimand Strategy

Same as [Section 6.6.1.1.1](#)

### 6.6.2.2.1.2. Population of Interest

Same as [Section 6.6.1.1.2](#)

### 6.6.2.2.1.3. Intercurrent Event Handling Strategy

Same as [Section 6.6.1.1.3](#)

## 6.6.2.2.2. Analysis Variables

### 6.6.2.2.2.1. Absolute Change from Baseline in Grip Strength at Week 52

The absolute change from baseline in the grip strength of the hands is derived with the formula below:

$$\begin{aligned} & \text{grip strength of the hands value at Post baseline visit} \\ & - \text{grip strength of the hands value at Baseline} \end{aligned}$$

The grip strength should be reported by dominant and non-dominant hand separately.

### 6.6.2.2.3. Covariance Structure Strategy

The unstructured covariance structure for the within-patient errors in the model will be applied first. The by-treatment-group option may will be added to the covariance pattern to improve the model fit as appropriate.

If the algorithm for unstructured covariance pattern does not converge, the following covariance structures will be tested in sequence until the model converges: heterogeneous Toeplitz, homogeneous Toeplitz, first-order autoregressive, compound symmetry, and variance component, until the model converges. The sandwich estimator will be used if there is convergence issue. If the model doesn't converge for all covariance structures listed above, some least significant factors or interaction terms ( $p > 0.05$ ) can be excluded from the model to achieve convergence. The revised model with fewer factors or interaction terms will be tested using the same sequence as specified above.

Sample SAS code:

*/\* excluding baseline visit \*/*

```
PROC MIXED DATA=MMRM (WHERE=(AVISITN>0));
  CLASS TRTP AVISIT;
  MODEL CHG = TRTP AVISIT TRTP*AVISIT BASE /DDFM=KR;
  REPEATED AVISIT /SUBJECT=SUBJID TYPE=UN GROUP=TRTP;
  LSMEANS TRTP /PDIFF CL;
  LSMEANS TRTP*AVISIT /PDIFF CL;
  ODS OUTPUT LSMEANS=MIXLSMNS DIFFS=MIXDIFS;
RUN;
```

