### 6.6. Efficacy Analyses

The primary and secondary endpoints will be tested using a fixed sequence procedure to preserve the study-wide error rate of 5%. Under the sequential analysis, the primary and secondary efficacy endpoints will be tested in a predefined sequence according to the order listed in Table 1 each at the usual alpha= 0.05 level of statistical significance. The testing will cease when a failure occurs in the pre-determined sequential hypothesis testing and all p-values for the subsequent testing will be considered nominal.

All analyses for efficacy endpoints will be performed for the mITT during the On-Study period (Section 5.3.1.1), unless noted otherwise. Sensitivity analysis on ITT will also be performed on primary and secondary endpoints as supportive evidence.

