**Table 1: Testing Sequence of Primary and Secondary Endpoints**

Testing Sequence	Endpoint
1 (primary endpoint)	Change in the total score of Performance of Upper Limb [(PUL) version 2.0], from baseline to Week 52.
2	Change in percent predicted Forced Vital Capacity (ppFVC) from baseline to Week 52, assessed by spirometry.
3	Change in the total score of Mid-level of PUL from baseline to Week 52
4	Change in the grip strength of the hands from baseline to Week 52, assessed by Hand-Held Myometry (HHM).
5	Change in Left Ventricular Ejection Fraction percentage (LVEF %) from baseline to Week 52, assessed by MRI.

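### The last-resort convergence rule for grip strength can remove treatment-by-visit, so that step 4 of the testing sequence would no longer test the Week 52 difference (low priority)

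*SAP*

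**What the plan says.** SAP 6.6 tests the endpoints of Table 1 in order, "each at the usual alpha= 0.05 level of statistical significance", and stops at the first failure. Grip strength change to Week 52 is step 4 and LVEF is step 5. SAP 6.6.2.2.2 names the grip variable as "Absolute Change from Baseline in Grip Strength at Week 52".

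SAP 6.6.2.2.3 gives the model as "MODEL CHG = TRTP AVISIT TRTP*AVISIT BASE /DDFM=KR". The sample code requests least-squares means both for treatment overall and for treatment-by-visit. No paragraph in 6.6.2.2 says which of the two is the confirmatory comparison.

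If the unstructured covariance fails, five simpler structures are tried: two Toeplitz forms, AR(1), compound symmetry and variance components. The next step is conditional: "If the model doesn't converge for all covariance structures listed above", then "some least significant factors or interaction terms" with p above 0.05 can be left out. After that, "The revised model with fewer factors or interaction terms will be tested using the same sequence as specified above". No term is protected.

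The fallback for the primary model (SAP 6.6.1.1.5, reused for the PUL MMRM in 6.6.1.2.1.5) has no rule for dropping terms by p-value.

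**The concern.** Treatment-by-visit is the only interaction in the grip model and the only source of a treatment difference specific to Week 52. If it is removed, one treatment coefficient applies to all post-baseline visits, and the p-value reported at step 4 belongs to a different hypothesis from the one in Table 1. That p-value also decides whether LVEF is tested confirmatorily.

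Two features make the rule hard to apply reproducibly. It operates only when no listed structure has converged, so there is no valid full fit from which to read the p-values. It also sets neither the order nor the number of terms to remove. And a non-significant interaction in a trial of this size is weak evidence that the effect is constant over visits.

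**Working it through.** **Inputs from the documents.** Post-baseline grip visits are Weeks 16, 28, 40 and 52 (SAP Table 9; grip is a muscle function test under Protocol Appendix 1, footnote j). The mITT set is expected to have 82 subjects, so 41 per arm (SAP section 7).

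**Inputs not in the documents (assumptions).** No SD, visit correlation, effect size or effect shape is given for grip. I borrow the standardised PUL effect, 2.0/2.9 = 0.69, and vary the covariance.

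**Step 1, the plan's own figures.** For a two-sided t-test with noncentrality 2.0/(2.9 × √(2/n)):
- n = 46 per arm gives 90.5% power (SAP 3.3 states 90%).
- n = 41 per arm gives 87.0% (SAP section 7 states 87%).

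Both reproduce. The large-sample normal version used below gives 87.7% at 41 per arm.

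**Step 2, what the reduced model estimates.** Let S be the covariance of the four visits. Without treatment-by-visit, the treatment coefficient is a weighted mean of the four visit differences with weights S⁻¹1/(1ᵀS⁻¹1). Under compound symmetry each weight is 0.25. For an effect growing linearly to Week 52, the common effect as a share of the Week 52 effect is (16 + 28 + 40 + 52)/(4 × 52) = 136/208 = 0.654.

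**Step 3, power for a linear effect.** The Week 52 test has noncentrality 0.69/√(2/41) = 3.12, hence 87.7%. Under compound symmetry with correlation 0.6, the SE ratio is √((1 + 3 × 0.6)/4) = 0.837. The common-effect noncentrality is 0.654 × 3.12/0.837 = 2.44, hence 68%. Results over six assumed covariances:

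| Assumed covariance | Weights, Weeks 16/28/40/52 | Common ÷ Week 52 effect | Power, common effect | P(interaction p > 0.05) |
|---|---|---|---|---|
| Compound symmetry 0.6 | 0.25/0.25/0.25/0.25 | 0.65 | 68% | 45% |
| AR(1) 0.7 | 0.385/0.115/0.115/0.385 | 0.65 | 71% | 68% |
| Random slope, 30% of Week 52 variance | 0.34/0.28/0.22/0.16 | 0.59 | 93% | 70% |
| Random slope, 50% | 0.43/0.31/0.19/0.07 | 0.52 | 85% | 63% |
| Random slope, 70% | 0.58/0.36/0.14/−0.08 | 0.40 | 70% | 53% |
| SD rising from 0.6 to 1, AR(1) 0.7 | 0.80/0.02/0.05/0.13 | 0.43 | 63% | 54% |

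Power moves in both directions. For an effect constant over visits, compound symmetry gives noncentrality 3.12/0.837 = 3.73, about 96%, which is above the Week 52 test.

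**Step 4, error rate.** With no effect at any visit, the common-effect test has a nominal 5% level. A simulation (6,000 trials per scenario, pooled unstructured covariance) gave about 6%. If instead the effect is present early and gone by Week 52, the Week 52 null is true but the common effect is not zero. The reduced test then rejects in 46% to nearly 100% of trials. Those figures ignore the p > 0.05 condition. In the simulation, the interaction was non-significant in 4%, 12% and 23% of such trials under three covariances, and the reduced model then rejected in 55%, 44% and 99.8%. The products are about 2%, 5% and 23%. For the six patterns above, the common estimate is uncorrelated with the visit contrasts, so the same product runs from 0.114 × 0.463 = 5% to 0.412 × 0.933 = 38%. None of these calculations conditions on non-convergence.

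**The case against.** The clause is close to dead text. It needs six structures to fail, and the last, variance components, means independent errors with at most one variance per arm. With about 82 subjects and four visits that should almost always converge. This stands, and it sets the priority.

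Grip is tested only after PUL, ppFVC and mid-level PUL have each succeeded. A grip effect at full size early and exactly zero at Week 52, alongside three positive results, is not a likely state. This also stands.

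A reader might infer that power always falls. The table and the constant-effect case show otherwise, and the documents give no grip inputs to settle it. A reader might also infer that treatment itself could be dropped as a least significant factor. The wording does not exclude it, but Table 1 and the section heading fix a treatment comparison at Week 52, so that is not a fair reading.

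The objection does not remove the core. When the rule is used, it permits a change of hypothesis inside a confirmatory sequence, on p-values that have no converged model behind them.

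**Conclusion.** The point holds as a low-priority correction. SAP 6.6.2.2.3 states a rule that, if ever reached, can replace the Week 52 grip difference with a precision-weighted effect common to Weeks 16 to 52. That is a simple average over visits only when the weights are equal, and in some assumed patterns Week 52 carries almost no weight.

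The size is illustrative. With 41 per arm, compound symmetry and a linearly growing effect, the common effect is about 65% of the Week 52 effect. Over the six assumed covariances it is 40% to 65%. The direction of the power change is not determined by the documents.

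A reader might infer that step 4 has a grossly inflated error rate. The documents do not support that. Error stays near 5 to 6% if there is no effect at any visit. It rises for the Week 52 null only if earlier visits differ, the interaction is also non-significant, and every covariance structure has already failed.

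**What to change.** In SAP 6.6.2.2.3, delete the sentence that allows terms with p above 0.05 to be excluded and the following one on the revised model. Replace them with: *Treatment, visit, treatment-by-visit and baseline are kept in every model; only the covariance structure may be simplified. The step 4 p-value is that of the Week 52 treatment difference from the treatment-by-visit least-squares means.* The second sentence is useful even if the fallback is never reached, because 6.6.2.2 does not name the confirmatory contrast.

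If a last resort is wanted after all structures fail, use ANCOVA of change at Week 52 on treatment and baseline, as SAP 6.6.2.3.3 does for LVEF. Its downside is that it uses only subjects with a Week 52 value and loses the information that earlier visits give under the missing-at-random assumption.

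The cost is two or three sentences of SAP wording, with no change to data collection or sample size.

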### 6.6.2.3. Continuous Secondary Endpoints with ANCOVA Model

#### 6.6.2.3.1.1. Estimand Strategy

Same as [Section 6.6.1.1.1](#)

#### 6.6.2.3.1.2. Population of Interest

Same as [Section 6.6.1.1.2](#)

#### 6.6.2.3.1.3. Intercurrent Event Handling Strategy

Same as [Section 6.6.1.1.3](#)

#### 6.6.2.3.2. Analysis Variables

##### 6.6.2.3.2.1. Change in Left Ventricular Ejection Fraction Percentage (LVEF %) from Baseline to Week 52, Assessed by MRI

##### 6.6.2.3.3. Population Summary for Treatment Comparison

The change in the LVEF% from baseline to Week 52 will be analyzed using an ANCOVA model, which contains terms for treatment, baseline LVEF measurements. The LSMean and corresponding SE for the change from baseline in LVEF at Week 52 will be estimated.

Sample SAS code:

```
/* excluding baseline visit */
```

```
PROC MIXED DATA=ANCOVA METHOD=ML;  
  CLASS TRTP;  
  MODEL CHG = TRTP BASE / DDFM = KR;  
  LSMEANS TRTP /PDIFF CL;  
RUN;
```

### 6.6.2.4. Analysis of A Composite of Endpoints

#### 6.6.2.4.1.1. Estimand Strategy

To evaluate the totality of the treatment effect in multiple muscle groups (i.e., skeletal, respiratory, and cardiac muscle), a composite endpoint will be used to combine the results from multiple outcomes including primary endpoint and 3 key secondary endpoints (PUL, ppFVC, Grip Strength, LVEF%) as a secondary analysis following the method introduced by Li, et al in 2020.

#### 6.6.2.4.1.2. Population of Interest

Same as [Section 6.6.1.1.2](#)

#### 6.6.2.4.1.3. Intercurrent Event Handling Strategy

Same as [Section 6.6.1.1.3](#)

#### **6.6.2.4.2. Analysis Variables**

The z-score is defined as LSmean of the treatment difference divided by its corresponding SE at week 52 from the primary analysis model. The mean z-score will be calculated sequentially across 4 endpoints (PUL, ppFVC, Grip Strength, LVEF%), namely, the mean z-scores for PUL + ppFVC, PUL + ppFVC + Grip Strength, PUL + ppFVC + Grip Strength + LVEF will be reported.

#### **6.6.2.4.3. Population Summary for Treatment Comparison**

The mean z-score will be calculated sequentially across 4 endpoints (PUL, ppFVC, Grip Strength, LVEF%) and p-value will be derived by a permutation method to rerandomize patient vectors of the observed values from the 4 endpoints in 1000 trials. A distribution of the mean z-score will be derived from these 1000 trials. A p-value will be computed from the z-score from this clinical trial against the backdrop of the random distribution of the 1000-trial z-scores. p-values corresponding to the z-scores for PUL + ppFVC, PUL + ppFVC + Grip Strength, PUL + ppFVC + Grip Strength + LVEF will be reported. If the p-value is  $< 0.025$  (1-sided), the composite endpoint is deemed to be statistically significant.

The method was introduced by Li, et al in 2020 [16].

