### **4.2. Secondary Endpoints**

- Change in percent predicted forced vital capacity (ppFVC) from baseline to Week 52, assessed by spirometry
- Change in the total score of Mid-level of PUL from baseline to Week 52
- Change in the Grip strength of the hands from baseline to Week 52, assessed by Handheld Myometry (HHM)
- Change in Left Ventricular Ejection Fraction percentage (LVEF %) from baseline to Week 52, assessed by MRI
- **Composite of endpoints**  
Mean observed z score for each of the 3 composite endpoints (PUL, ppFVC), (PUL, ppFVC, Grip Strength), (PUL, ppFVC, Grip Strength, LVEF%).

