- MMRM ([Section 6.6.1.2.1](#)), Cumulative Loss of Function Analysis ([Section 6.6.1.2.8](#)) are added as sensitivity analyses for the primary efficacy endpoint.
- Added the composite of endpoints - mean observed z scores sequentially across 4 endpoints (PUL, ppFVC, Grip Strength, LVEF%) at week 52, namely, the mean z-scores for PUL + ppFVC, PUL + ppFVC + Grip Strength, PUL + ppFVC + Grip Strength + LVEF%, to the secondary endpoint. Analysis with the Composite of Endpoints ([Section 6.6.2.4](#)) is added as additional analysis for PUL.
- Change in the total score of Mid-level of PUL from baseline to Week 52 is added as a secondary endpoint.

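### Three composite secondary endpoints sit outside the Table 1 sequence and have their own ungated significance rule, so the stated 5% study-wide error rate does not hold

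*SAP*

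**What the plan says.** Four places in the SAP bear on this.

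- **Section 6.6** states the guarantee: "The primary and secondary endpoints will be tested using a fixed sequence procedure to preserve the study-wide error rate of 5" percent. Testing follows Table 1 and stops at the first failure, after which "all p-values for the subsequent testing will be considered nominal".
- **Section 4.2** includes among the secondary endpoints "Mean observed z score for each of the 3 composite endpoints": PUL with ppFVC, then with grip strength added, then with LVEF% added. Section 7 records the change: "Added the composite of endpoints - mean observed z scores sequentially across 4 endpoints", placing them with the secondary endpoints.
- **Table 1**, headed "Testing Sequence of Primary and Secondary Endpoints", has five steps: PUL total, ppFVC, PUL mid-level, grip strength and LVEF%. No composite appears. Section 6.6.2 sends the secondary endpoints back to the Table 1 order, which gives the composites no position.
- **Section 6.6.2.4.3** derives a permutation p-value for each composite and says that at one-sided p < 0.025 "the composite endpoint is deemed to be statistically significant". It sets no precondition, no division of alpha and no order of claims.

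Protocol Section 8.3.1 makes testing of the secondary endpoints conditional on a significant primary result. The composites are not in the protocol; the SAP added them.

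**The concern.** By Sections 4.2 and 7 the composites belong to the family that Section 6.6 says it protects. By Table 1 they are outside the procedure that provides the protection. Section 6.6.2.4.3 then allows a significance statement on them whatever happened earlier.

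The conflict matters most if PUL fails. Section 6.6 then allows no further confirmatory claim from the sequence, while Section 6.6.2.4.3 still allows a composite that contains PUL to be called significant. That is when such a claim would be most tempting, and the 5% statement would not cover it.

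**Working it through.** **Inputs from the documents**

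- Primary test: two-sided alpha 0.05 (SAP 6.6.1), so PUL rejects when |Z₁| > 1.96.
- Each composite: one-sided 0.025 (SAP 6.6.2.4.3), so it rejects when its standardised mean z exceeds 1.96. The permutation refers each mean z to its own null distribution, which is what the standardisation represents.
- Composites: nested means of the first 2, 3 and 4 of PUL, ppFVC, grip strength and LVEF% (SAP 6.6.2.4.2).

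**Assumption.** The documents give no correlation between the endpoint z-scores. A common correlation ρ is varied from 0 to 1. All results are under the global null (no effect on any endpoint).

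**Step 1: the plan's own figure.** With Table 1 alone, nothing is tested unless PUL rejects, so P(any false claim) = P(|Z₁| > 1.96) = 5.0%. The stated rate reproduces for the five listed steps.

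**Step 2: add the composite rule as written.** The error rate becomes P(|Z₁| > 1.96, or a composite > 1.96). The Bonferroni ceiling is 5.0% + 3 × 2.5% = 12.5%. The true value is lower because every composite contains PUL and the composites overlap.

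**Step 3: two rules with a direct formula.** The correlation between Z₁ and the standardised mean of k endpoints is √((1 + (k − 1)ρ)/k), and

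P(any false claim) = 5.0% + 2.5% − P(both reject).

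- *Composites claimed only in listed order.* The first composite (k = 2) gates the other two, so only it adds error. At ρ = 0 its correlation with Z₁ is √(1/2) = 0.707 and P(both) is 0.84%, giving 7.5% − 0.84% = 6.66%.
- *Four-part composite only* (k = 4). At ρ = 0 the correlation is √(1/4) = 0.5 and P(both) is 0.46%, giving 7.5% − 0.46% = 7.04%.

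**Step 4: any of the three may be claimed.** This was simulated with several million draws of four equicorrelated normal z-scores.

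| Chance of any false claim | ρ = 0 | 0.3 | 0.5 | 0.9 | 1.0 |
|---|---|---|---|---|---|
| Table 1 only | 5.0% | 5.0% | 5.0% | 5.0% | 5.0% |
| Primary, or any composite | 8.8% | 7.8% | 7.2% | 5.9% | 5.0% |
| Primary, or composites in listed order | 6.7% | 6.4% | 6.2% | 5.5% | 5.0% |
| Primary, or four-part composite only | 7.0% | 6.7% | 6.4% | 5.6% | 5.0% |

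**Step 5: composite claims after PUL has failed.** Subtracting the 5.0% for the primary gives the chance of a false composite claim when PUL is not significant. It is 3.8%, 2.8%, 2.2% and 0.9% at ρ = 0, 0.3, 0.5 and 0.9 if any composite counts, and 1.7%, 1.4%, 1.2% and 0.5% if they are taken in order.

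**Step 6: false claims in the drug's favour.** Table 1 allows 2.5%. With any composite claimable this becomes 6.3% at ρ = 0, 4.7% at 0.5 and 3.4% at 0.9.

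**The case against.** The best reply is that the composites were meant as supportive. The Section 7 bullet that adds them also describes them as a further analysis relating to PUL, Section 6.6.2.4.1.1 calls the work a secondary analysis of the totality of effect, and Section 6.6.2.4.3 says the p-values will be reported. If they are supportive, nothing is inflated. But the same bullet places them among the secondary endpoints, no section calls them nominal or exploratory, and a significance threshold has no purpose for a purely descriptive result. If supportive was the intent, the SAP needs only to say so.

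A second reply is that Section 6.6 already makes them nominal after a failure. That clause concerns later tests in the Table 1 sequence, where the composites have no place. If it is read more widely to include them, Section 6.6.2.4.3 contradicts it. Either way the text needs correcting.

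A third is that the word used for building the composites one component at a time implies a testing order. It describes how the mean z-score is assembled. Even read as an order, it does not tie the first composite to the primary, and the rate is still 6.7% to 5.5%.

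Two points do stand. Section 6.6.2.4.1.1 speaks of a single composite of all four outcomes, so 8.8% to 5.9% is the least favourable reading and 7.0% to 5.6% may be nearer the intent. And the size of the excess depends on the assumed correlation, disappearing only at exactly 1.

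**Conclusion.** The concern holds. As written, the SAP guarantees 5% for a family that includes the composites and then gives those composites a route to significance outside the procedure that supplies the guarantee. Under the global null with equal correlation between endpoints, the rate exceeds 5% under each of the three claim rules for any correlation from 0 up to, but not including, 1. Over 0 to 0.9 it lies between 5.5% and 8.8%, depending on the rule. The excess is moderate and well short of the 12.5% ceiling. The primary test and the other four Table 1 steps keep their stated error control; only claims on the composites are affected. Because the stated guarantee is incorrect as it stands, it should be corrected before unblinding.

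**What to change.** Choose one of the following.

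1. **Make the composites nominal.** State in Sections 4.2 and 6.6.2.4 that the three composites are supportive with nominal p-values, and delete the significance sentence in Section 6.6.2.4.3.
2. **Put them in the sequence.** Append them to Table 1 as steps 6 to 8 in a stated order, each tested only if every earlier step has succeeded. State there that their one-sided 0.025 criterion applies within a sequence otherwise run at 0.05, so that sidedness is explicit.

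Under either option no false claim is possible unless PUL first rejects, so the study-wide rate returns to 5.0%. The change is wording only, with no effect on design, data collection or the primary analysis. The price is that no confirmatory composite claim can be made when an earlier step fails; under option 2 a composite would be tested only after all five present steps had succeeded.

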#### **6.6.2.5. Assessments by ITT populations of secondary endpoints:**

Assessments by ITT populations of secondary endpoints will be considered as sensitivity analysis for these secondary endpoints. Summary of the following endpoints will also be conducted on the ITT population. The change from baseline to Week 52 in these endpoints will be summarized by analysis visit and analyzed using the RCM or MMRM or ANCOVA model as described in corresponding sections in [Section 6.6.2](#).

- Change in percent predicted forced vital capacity (ppFVC) from baseline to Week 52, assessed by spirometry
- Change in the total score of Mid-level of PUL from baseline to Week 52
- Change in the Grip strength of the hands from baseline to Week 52, assessed by Handheld Myometry (HHM)
- Change in Left Ventricular Ejection Fraction percentage (LVEF %) from baseline to Week 52, assessed by MRI
- Sequential composites of endpoints - PUL + ppFVC, PUL + ppFVC + Grip Strength, PUL + ppFVC + Grip Strength + LVEF

